#### 4.5.4.3 Treatment Phase Visits: Weeks 2-4

The following assessments and activities are performed at these visits:

- Medical history changes from previous visit
- Physical examination changes from previous visit
- Assess concomitant medications, changes from previous visit and prohibited therapies
- ABI, SPP, TCOM, TBI, PVR measurement or Arterial Doppler Study will be obtained (see Appendices B-D)
- Vital Signs
- Pain assessment (see section & 5)
- Assess blood glucose
- Assessment of offloading
- Target ulcer foot neuropathy Semmes Weinstein 10-point test; (see section 8.9)
- Check for any changes in the subject's health and assess them for any adverse effects and adverse events
- Target ulcer closure assessment will be determined by a site Investigator
  - If the target ulcer is 100% re-epithelialized, the subject will exit study at the conclusion of the visit (the visit will be considered EOS1). Please perform all applicable assessments and study procedures associated with EOS1.
- Target ulcer Assessments
- Check for signs of clinical infection. If a clinical diagnosis of infection has been made, then the subject can be treated with oral antibiotics, but topical antibiotics or antimicrobial dressings CANNOT be used on the target ulcer (see section 8.6.3)
- Clean the target ulcer

- Debridement of the target ulcer if applicable (see Appendix E)
- Digital imaging of the target ulcer
- Record target ulcer measurements
- Apply appropriate treatment to the index ulcer:
  - Apply SOC therapy with Helicoll® Group 1
  - Apply SOC therapy with Epifix® or Grafix® Group 2

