## **10.1 SOC Adverse Events**

Since this a post market study involving commercially available SOC dressings of FDA cleared and approved medical devices; adverse events associated with their use may also require reporting to FDA along with the possible reason for the failure of the treatment which may include product handling and other details.

An AE is defined as any unfavorable or unintended sign, symptom or disease that occurs or is reported by the subject to have occurred, or a worsening of a pre-existing condition related to the procedure or medical treatment (device/drug) used. All AEs related to the study procedure or medical treatment, including intercurrent illnesses, must be recorded in the subject's medical records and on the CRF. CTCAE v5.0 will be used for AE reporting.

AEs will be defined as those events that occur after the first study treatment is applied at TV1, through the final study visit. A description of the AE along with the onset date, end date, severity, action taken, treatment, outcome, likely cause and relationship to the study procedure or products will be recorded in the CRF.

AEs associated with each treatment arm will be tabulated and compared at the end of the study. AEs will be elicited through direct questioning, subject reports, and physical examination.

An abnormal laboratory test result is not by itself considered to be an AE unless the Investigator considers the finding of clinical significance that should be reported in such a manner.

The Investigator is responsible for assessing the relationship of the AE to the procedure or medical treatments used and the seriousness and expectedness of the AE at the time of occurrence. A medically qualified person appointed by the Sponsor will also assess this once the Sponsor has been notified of an AE. For enrolled subjects, all AEs that occur during the trial will be documented on the AE CRF.

AEs reported during the study should be followed to resolution of the AE or within thirty days from the end of the study. A final assessment of the outcome will be made at that time.

Each AE related to the study procedure or medical treatment used will be categorized as "serious" or "not serious," based on the definition of a serious adverse event (SAE). A SAE is defined as an AE resulting in at least one of the outcomes described in Section 10.1.3.

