The PP population will consist of randomized subjects with analysis conducted according to treatment received. The following subjects will be excluded: (a) subjects randomized but later found to be ineligible for the study because they failed to meet all inclusion and exclusion criteria; (b) subjects who did not complete the study; and (c) subjects with major protocol violations.

Safety Population

The safety population will be all subjects who were randomized and received at least one treatment.

Definitions

Baseline

For all parameters, baseline will be defined as the last available data point before the first treatment, which occurs at TV1.

Visit window data including study endpoints

For each weekly visit a window of ± 2 days will be adopted for data. If a specified time endpoint is outside of the window the last available visit data prior to the specified endpoint will be used.

Healing of Index Ulcer

Healing is defined as complete epithelialization of the ulcer without drainage observed in the index ulcer at two separate visits 2 weeks apart. If a subject fails this healing confirmation visit then they can continue in the trial with their assigned treatment provided that the index wound did not heal at the EOS visit.

Date of healing

The date of healing is defined as the date of the first assessment of index ulcer healing provided the index ulcer is still healed 2 weeks later.

Percentage area reduction from baseline

The percent change in the surface area of the Index Ulcer (PAR) will be calculated using the following formula:

((A1-A2)/A1)*100

Where A1 is the baseline area (at randomization), and A2 is the area at the specified time point.

Statistical Methodology

Missing data

Missing data may be the result of missed visits, subjects lost to follow-up or who have died, and may be endpoint data or covariate data.

The outcome of complete wound healing will be scored as **not** healed for the following events:

• The subject dies

- The subject has an amputation that affects the index ulcer
- The subjects is lost to follow-up
- The subjects is withdrawn from the trial
- The subject withdraws consent.

Missing PAR endpoint data within 5 weeks from TV1 will be not imputed.

Data QC

- 1. Inspect for accuracy of input:
 - 1.1. Plausible values
 - 1.2. Outliers or out-of-range values
- 2. Evaluate degree and distribution of missing data; for missing non-endpoint, out-of-range or non-plausible data, query PERI.

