- 4. Number of applications of the intervention product for healed wounds only by treatment group.

Analysis will be done for the ITT population.

Safety Analysis

The following will be conducted:

Summary statistics for each treatment group:

- Count of AEs per treatment group/per patient
- Summary rates per group
- Notes of unexpected occurrences during the study; relevant decisions made) (text in report)
- Counts of SAEs/AEs by treatment group (listing of subjects); see shell Table 4.

- Complete listing of all AEs by subject, system organ class and preferred term(s). SAEs will be **bolded** in the listing (see shell Table 5).
- Counts of AEs by severity and relatedness to intervention product (see shell Table 6).

Shell Figure 1. CONSORT subject flow chart. EP: Epifix; HC: Helicoll.

Shell Table 1. Patient-related variables, except for comorbidities and concomitant drugs. Figures in parentheses will be percentage for categorical variables and standard deviation (SD) of the mean for continuous variables; for non-normal variables, such as initial wound area, medians and interquartile ranges (IQR) will be added.

Variable	Epifix	Helicoll	р
Age (years)	XX.X (XX.XX)	XX.X (XX.XX)	XX
Race			
Caucasian	X (X%)	X (X%)	
African American	X (X%)	X (X%)	XX
Other	X (X%)	X (X%)	
Ethnicity			
Hispanic	X (X%)	X (X%)	XX
Not Hispanic	X (X%)	X (X%)	
Gender			
Male	X (X%)	X (X%)	XX
Female	X (X%)	X (X%)	
BMI	XX.X (XX.XX)	XX.X (XX.XX)	XX
Smoker			
Current	X (X%)	X (X%)	
Former	X (X%)	X (X%)	XX
Never smoked	X (X%)	X (X%)	
HbA1c (%)			
At randomization	XX.X	XX.X	XX
Creatinine (mg/dL)	XX.X (XX.XX)	XX.X (XX.XX)	XX
Diabetes duration (years)	XX.X (XX.XX)	XX.X (XX.XX)	XX
Subject age when first DFU			
appeared (years)	XX.X (XX.XX)	XX.X (XX.XX)	XX
Prior DFU count	XX.X (XX.XX)	XX.X (XX.XX)	XX
Other concurrent DFUs (at			
screening	X (X%)	X (X%)	XX
History DFU recurrence	X (X%)	X (X%)	XX
Amputations, minor			
0	X (X%)	X (X%)	
1	X (X%)	X (X%)	
2	X (X%)	X (X%)	XX
3	X (X%)	X (X%)	
≥4	X (X%)	X (X%)	
Major amputations	X (X%)	X (X%)	XX

Variable	Epifix	Helicoll	р
Foot deformities			
Deformity 1	X (X%)	X (X%)	XX
{Continue for all subjects			
with identified different			
deformities}			

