Shell Table 2. Wound-related variables. Figures in parentheses will be percentage for categorical variables and standard deviation (SD) of the mean for continuous variables; for variables that have a non-normal distribution of values, such as initial wound area, medians and interquartile ranges (IQR) will be added.

Variable	Epifix	Helicoll	р
Wound area (cm ²)	XX.X (XX.XX)	XX.X XX (XX)	XX
	XX (XX)	XX (XX)	
Wound age (weeks)	XX.X (XX.XX)	XX.X XX (XX)	XX
	XX (XX)	XX (XX)	
Vertical location			
Plantar	X (X%)	X (X%)	XX
Dorsal	X (X%)	X (X%)	
Position			
Medial	X (X%)	X (X%)	XX
Lateral	X (X%)	X (X%)	
Anatomical location			
Тое	X (X%)	X (X%)	
Forefoot	X (X%)	X (X%)	
Midfoot	X (X%)	X (X%)	XX
Heel	X (X%)	X (X%)	
Ankle	X (X%)	X (X%)	
Offloading type:			
Type 1	X (X%)	X (X%)	XX
{Continue with			
summary statistics			
for all subjects with			
identified different			
types of offloading}			
Number of	XX.X (XX.XX)	XX.X (XX.XX)	XX
debridements			

Comorbidity	Epifix	Helicoll	р
СКD	X (X%)	X (X%)	X (X%)
Hypertension	X (X%)	X (X%)	X (X%)
PAD	X (X%)	X (X%)	X (X%)
CHF	X (X%)	X (X%)	X (X%)
Leg edema	X (X%)	X (X%)	X (X%)
Restricted mobility*	X (X%)	X (X%)	X (X%)
Venous disease	X (X%)	X (X%)	X (X%)
Peripheral neuropathy	X (X%)	X (X%)	X (X%)
Any psychiatric condition	X (X%)	X (X%)	X (X%)
Comorbidity count**	XX.X	XX.X	XX

Shell Table 3. Selected comorbidities noted at first physical examination by treatment group.

*Restricted mobility: any subject who uses a walker, wheelchair, crutches or canes, and/or has an inability to move freely because of a physical or mental disability, handicap or restriction.

**Based on all identified comorbidities from medical history.

Shell Table 4. Count of SAEs (bolded) and AEs by subject, and totals by treatment group (figures in parentheses represent percentage of total AEs).

AE Category	Epifix	Helicoll
Subject ID	XX-XXX	XX-XXX
SAE count	х	x
{Continue for all subjects with SAEs}		
TOTAL (SAEs)	xx (xx)	xx (xx)
Subject ID	XX-XXX	XX-XXX
AE count	х	x
{Continue for all subjects with AEs}		
TOTAL (AEs)	xx (xx)	xx (xx)

Shell Table 5. Categorization of AEs by medDRA terms for each subject. For AEs categorized as SAEs, **listings will be bolded**.

TEAE Category	Epifix	Helicoll
Subject ID	XX-XXX	XX-XXX
System organ class	Text	Text
Preferred term(s)	Text	Text
{Continue for all system organ classes for		
each subject. Start a new page for each		
subject}		

Shell Table 6. Categorization of AEs by severity and relatedness.

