Figures in parentheses represent percentages for each treatment group.

AE Category	Epifix	Helicoll
Severity		
Mild	xx (xx)	xx (xx)
Moderate	xx (xx)	xx (xx)
Severe	xx (xx)	xx (xx)
Life-threatening	xx (xx)	xx (xx)
Fatal	xx (xx)	xx (xx)
Relatedness		
Not related	xx (xx)	xx (xx)
Unlikely to be related	xx (xx)	xx (xx)
Possibly related	xx (xx)	xx (xx)
Probably related	xx (xx)	xx (xx)
Definitely related	xx (xx)	xx (xx)

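### SAP Shell Table 4 gives AE percentages per event rather than per subject, and the planned AE rates have no stated denominator or time base although healed subjects leave early

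*SAP*

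**What the plan says.** **Shells.** Shell Table 4 lists SAE and AE counts by subject ID, then gives arm totals with a bracketed percentage. Its caption says "figures in parentheses represent percentage of total AEs". Shell Table 5 is a listing without percentages. Shell Table 6 (severity and relatedness) says "Figures in parentheses represent percentages for each treatment group", without saying whether the base is events or subjects.

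**Text.** The SAP's Safety Analysis section also plans "Count of AEs per treatment group/per patient" and "Summary rates per group". Neither has a denominator or a time unit. Under Patient Populations the SAP states: "The safety population will be all subjects who were randomized and received at least one treatment". The Safety Analysis section does not name that population, and no shell has a row for subjects with at least one AE or SAE.

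**Follow-up.** Protocol 4.5.4.3 says "If the target ulcer is 100% re-epithelialized, the subject will exit study at the conclusion of the visit". Protocol 10.1 counts as AEs those that "occur after the first study treatment is applied at TV1, through the final study visit", and says that AEs will be compared between arms at the end of the study. The SAP, under Healing of Index Ulcer, requires healing to be seen at two visits two weeks apart. Table 1 of the protocol schedules no such visit after closure.

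**The concern.** A between-arm comparison of AEs needs a denominator that reflects how many people were at risk. The only percentage whose base is stated divides by events. It mixes the number of subjects affected with the number of events per affected subject, and the SAE percentage also depends on how many non-serious events were recorded. With about 12 subjects per arm, one subject with several events can move it a good deal.

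A second, separate matter is observation time. Under the protocol a healed subject stops contributing AEs at the closure visit. The length of the AE window therefore depends on the efficacy outcome, and raw counts may be lower in an arm that heals faster even if the AE hazard is the same. Neither document plans person-time. At stake is how the safety table reads, not a formal safety conclusion.

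**Working it through.** The plan states no AE rate, and the 24 subjects are a convenience sample, so there is no figure to reproduce. The checks below are arithmetic on the table definitions.

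**Inputs from the documents**
- 24 subjects, half to each group (protocol synopsis), taken as 12 per arm.
- End of study at 4 weeks from treatment in Protocol Table 1 (28 days), or 5 weeks after randomization in the SAP's Brief Trial Description (35 days). Both are used.

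**Assumed, because the documents give none:** AE counts, healing proportions and closure days.

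**1. What the Shell Table 4 percentage measures**

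*Pooled reading* (arm's AEs / all AEs). Arm A has 6 subjects with 1 AE each. Arm B has 2 subjects with 10 AEs in all.
- Share of events: A 6/16 = 37.5%, B 10/16 = 62.5%.
- Subjects affected: A 6/12 = 50.0%, B 2/12 = 16.7%. The order reverses.

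*Within-arm reading* (count / arm's own AEs). The AE total is 100% in both columns by construction. For SAEs, suppose A has 3 SAEs among 12 AEs and B has 2 among 4, with one SAE per subject.
- Planned percentage: A 3/12 = 25%, B 2/4 = 50%.
- Subjects affected: A 3/12 = 25.0%, B 2/12 = 16.7%. The order reverses.
- The same data pooled: A 3/16 = 18.8%, B 2/16 = 12.5%. The order does not reverse.

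Whether a given data set misleads therefore depends on a reading that the caption leaves open.

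**2. How often the order differs**

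The simulation used equal true arms of 12, a mean of 0.5 or 1.0 AEs per subject, Poisson or negative binomial counts (dispersion 0.3, 0.5 or 1.0), and 100,000 runs per setting. The arm with more affected subjects had fewer AE events in 4.5% to 15.7% of trials. This covers AE totals, as on the pooled reading. It does not cover the within-arm SAE percentage.

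**3. Observation time**

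Person-days per arm = healed × closure day + unhealed × full follow-up.

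| Follow-up | Closure day | Healed, faster vs slower arm | Person-days | Ratio |
|---|---|---|---|---|
| 28 | 14 | 8 vs 4 | 8×14 + 4×28 = 224; 4×14 + 8×28 = 280 | 0.800 |
| 28 | 21 | 6 vs 4 | 6×21 + 6×28 = 294; 4×21 + 8×28 = 308 | 0.955 |
| 35 | 14 | 9 vs 3 | 9×14 + 3×35 = 231; 3×14 + 9×35 = 357 | 0.647 |
| 28 | 14 | 6 vs 6 | 252; 252 | 1.000 |

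The second and third rows are the extremes of the unequal-healing scenarios tried: 4.5% to 35% less person-time in the faster-healing arm. At an equal AE hazard, the expected raw count falls by the same share. With equal healing there is no gap.

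**4. If healed subjects stay for the SAP's confirmation and AEs are collected until then**
- Closure at day 14, confirmation at day 28, follow-up 28 days: 12×28 = 336 person-days in each arm, so no gap.
- Closure at day 14, follow-up 35 days, 9 vs 3 healed: 9×28 + 3×35 = 357 against 3×28 + 9×35 = 399, ratio 0.895. The gap falls from 35% to 10.5%.
- Closure at day 21, follow-up 28 days: confirmation at day 35 would fall after the last scheduled visit.

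**The case against.** The strongest reply is that the subject-level information is already there. Shell Table 4 lists every affected subject by ID, with raw counts beside the percentages, and the SAP also plans per-patient counts and group rates. With about 12 per arm, a careful reader can count the subjects affected. That stands, and it is why the consequence is modest. It does not give the printed percentage a useful meaning, and it does not define the planned rates.

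A reader might infer more: that the AE tables as a whole will make the arm with more affected subjects look safer. The documents do not support that. Only Shell Table 4 states an event base. Shell Table 5 has no percentages, and the base of Shell Table 6 is undefined rather than wrong. A bracketed percentage in the AE total row would be pointless within arm, which points at least as much to a pooled total, and some reversals disappear on that reading. Where a reversal is possible, it is the less common outcome.

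A reader might also join the two mechanisms. They are separate: early exit lowers counts in the faster-healing arm, which need not be the arm with more affected subjects. Nor is any particular exposure gap established. It rests on assumed healing and on an unresolved difference between protocol and SAP. The protocol's 30-day provision does not remove the issue, because it concerns follow-up of AEs already reported.

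Finally, exposure adjustment could be called optional with 24 subjects and at most 4 to 5 weeks of follow-up. That is fair as to importance. But the SAP already promises rates, and a rate needs a base.

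**Conclusion.** The point holds in a limited form. The Shell Table 4 percentage does not measure risk per subject on either reading. The base of Shell Table 6 and the planned group rates are undefined. The safety population is not named as the denominator of any AE shell, although AEs are to be compared by arm. The order of the arms can differ from the order by subjects affected. For AE totals this happened in about 5% to 16% of simulated trials with equal arms, at assumed means of 0.5 to 1.0 AEs per subject.

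Outcome-dependent follow-up is a second, separate weakness: 4.5% to 35% less person-time in a faster-healing arm over the assumed unequal-healing scenarios, none with equal healing, and possibly little or none if healed subjects remain under observation until confirmation.

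The consequence is modest. The trial has 24 subjects, tests no endpoint hypotheses and has no formal safety objective.

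**What to change.** 1. In Shell Table 4, replace the percentage of events with the number and percentage of safety-population subjects with at least one AE and with at least one SAE, by arm, with N in the column heads. Keep the event counts and the listing by subject ID.
2. In Shell Table 6, state the same subject denominator, with a rule for a subject with several events (for example, counted once at the highest severity).
3. Define the planned group rates as events per subject-week from first treatment to last visit, by arm.
4. Reconcile the protocol's exit at closure with the SAP's two-visit healing confirmation, and state until when AEs are collected for healed subjects.

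Items 1 to 3 are a free improvement: edits to shells and one definition, with no added subjects, visits or assessments. First treatment is at TV1, visits are dated, Protocol 10.1 already records AE onset dates, and the SAP already reports the week of discontinuation. Item 4 needs the protocol and SAP authors to agree on one text. All four should be settled before database lock.

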### 10.1.1 AE Severity Assessments

The guidelines outlined in CTCAE v4.0 will be used for severity assessments. Note: the term "severe" is a measure of intensity and that a severe AE is not necessarily serious. Table 5 below provides guidance on determining the severity of an AE.

| Version 1.0 |  |  |  |
|-------------|--|--|--|

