### TABLE 5: AE SEVERITY GRADING SCALE

| Severity Grade       | Description  |
|----------------------|--|
| Mild (1)             | Awareness of sign, symptom, or event, but easily tolerated;        |
|                      | does not interfere with usual daily activities or tasks.           |
| Moderate (2)         | Discomfort is enough to cause interference with usual daily        |
|                      | activity. It may warrant therapeutic intervention.                 |
| Severe (3)           | Incapacitating: inability to perform usual activities and daily    |
|                      | tasks; significantly affects clinical status; requires therapeutic |
|                      | intervention.  |
| Life-threatening (4) | Emergency treatment required, life-threatening, death.             |

A grade of 1-4 is assigned by the Investigator to each AE.

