### 10.1.2 AE Causality Assessments

AEs will be assigned a relationship (causality) to the study procedure or medical treatments. The Investigator will be responsible for determining the relationship between an AE and the study procedure or medical treatment. The type of event, organ system affected and timing of onset of the event will be factors in assessing the likelihood that an AE is related to the study procedure or medical treatment. The relationship of AEs to study procedures or medical treatments will be classified as follows:

- Not Related: No relationship exists between the AE and the study procedure or medical treatment. The event is attributed to a pre-existing medical condition or an inter-current event unrelated to the study procedure or medical treatments.
- Possibly Related: Follows the study procedure or medical treatment but may have developed as a result of an underlying clinical condition or treatments/interventions unrelated to the study.
- Probably Related: Follows the study procedure or medical treatment but is unlikely to have developed as a result of the subject's underlying clinical condition or other treatment or other interventions.
- Definitely Related: Follows the study procedure or medical treatment and physical evidence shows a convincing relationship to the study procedure or medical treatment.
- Unknown: Follows the study product or medical treatment, but unable to determine the relationship to the study procedure or medical treatment.

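### SAP Shell Table 6 does not match the protocol's adverse event scales: it has no 'Unknown' row, an 'Unlikely' row the protocol does not collect, and a 'Fatal' row with no stated source

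*SAP*

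**What the plan says.** **Relatedness.** Protocol 10.1.2 introduces its list with "The relationship of AEs to study procedures or medical treatments will be classified as follows" and gives five categories: not, possibly, probably and definitely related, and unknown. The last is defined as "Follows the study product or medical treatment, but unable to determine the relationship to the study procedure or medical treatment".

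**Severity.** Protocol Table 5 has four grades: mild, moderate, severe and life-threatening. Grade 4 is described as "Emergency treatment required, life-threatening, death". The line below the table says "A grade of 1-4 is assigned by the Investigator to each AE". Protocol 10.1.1 states "The guidelines outlined in CTCAE v4.0 will be used for severity assessments", while section 10.1 states "CTCAE v5.0 will be used for AE reporting".

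**Planned output.** The SAP's Safety Analysis section lists this item: "Counts of AEs by severity and relatedness to intervention product (see shell Table 6". The shell has five relatedness rows: not, unlikely ("Unlikely to be related"), possibly, probably and definitely. It has five severity rows: mild, moderate, severe, life-threatening and fatal.

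**The concern.** A table shell tells the programmer which categories exist and where each record goes. Here one category that the investigator may use has no place in the table, and one row of the table is not a category that the investigator may use. On severity, a single protocol grade has to feed two rows, with no rule for dividing it.

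This matters because no other planned output shows either attribute. Shell Table 4 gives counts of AEs and serious AEs. Shell Table 5 lists system organ class and preferred term. If an event coded unknown is left out of Shell Table 6, no specified output shows that its relationship could not be determined. A reader of the safety results would see relatedness rows that fall short of the AE total, without being told why.

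**Working it through.** The plan gives no figure to reproduce. The check sets the category lists side by side.

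**Step 1. Relatedness**

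| Category | Protocol 10.1.2 | SAP Shell Table 6 |
|---|---|---|
| Not related | yes | yes |
| Unlikely | no | yes |
| Possibly | yes | yes |
| Probably | yes | yes |
| Definitely | yes | yes |
| Unknown | yes | no |

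Four of the protocol's five categories have a row. Unknown has none. The unlikely row receives no data if the case report form (CRF) follows the protocol's list; the CRF is not among the documents.

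**Step 2. Severity**

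| Category | Protocol Table 5 | SAP Shell Table 6 |
|---|---|---|
| Mild | grade 1 | row |
| Moderate | grade 2 | row |
| Severe | grade 3 | row |
| Life-threatening | grade 4 | row |
| Fatal | within grade 4 | separate row |

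Four of the SAP's five rows match in name. The grade alone cannot divide grade 4 between the last two rows.

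**Step 3. Is there a mapping rule?** Neither document has one. Protocol 9.2 says that departures from its analyses will be described in the SAP, but the SAP does not mention this change of categories.

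**Step 4. Can deaths be identified by other means?** Yes. Protocol 10.1 lists outcome as a CRF item separate from severity. Protocol 10.1.3 makes death a criterion for a serious AE. The SAP's list of general analyses (item 4) reports deaths in total and by group, with week and reason. The SAP does not say that the fatal row of Shell Table 6 uses any of these.

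**Step 5. Size.** Let N be the number of AEs in an arm and U the number coded unknown. The relatedness rows then sum to N − U, so the share missing is U/N. The documents give neither N nor U. If U = 0, nothing is missing. If U = 1 and N is assumed to be 5, 10 or 20, the missing share is 1/5 = 20%, 1/10 = 10% or 1/20 = 5%. These values only show how sensitive a small trial is to one event; they are not estimates.

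**The case against.** The strongest reply is that this is a labelling slip in a descriptive shell, and that the data survive it. The SAP says all collected data will be reported and analysed. An unknown AE still enters the counts per group and per patient, so a shortfall in Shell Table 6 would show against those totals. Most rows agree with the protocol, and an empty unlikely row does no harm. The table falls short only if an unknown code is used, or if a death occurs and is not separated using outcome. The protocol also states that the study has no formal safety objective, and no endpoint is tested. These arguments stand, and they make the point minor. They do not remove it: a visible shortfall is still unexplained, and the output meant to show relatedness still has no place for a collected code.

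A second reply is that Table 5 is offered as guidance, with CTCAE named as the source, so the four grades may not be final. That is fair as far as it goes. However, the sentence below the table says plainly which grades the investigator assigns, and the protocol names two CTCAE versions. This is a reason to settle the severity scale in the protocol as well.

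Three stronger readings are tempting, and the documents do not support them.

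- A reader might infer that unknown events would be recoded as unlikely, which would understate possible product relation. No document prescribes any recoding.
- A reader might infer that a death would be counted as life-threatening while the fatal row shows zero. The SAP never says that the fatal row is filled from the 1 to 4 grade, and outcome and the serious AE criterion can both supply it.
- A reader might want unknown events counted with the related ones. The SAP plans no related total, so a separate row is enough.

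**Conclusion.** Shell Table 6 is wrong as written, and the point is minor. One of the protocol's five relatedness codes has no row, one relatedness row is not a protocol category, and one of five severity rows has no stated source. Any AE coded unknown would be missing from the only planned summary of relatedness. Deaths remain identifiable and are reported elsewhere by group, so on severity the defect is an unstated derivation, not lost information.

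The conclusion about the unlikely row assumes that the CRF uses the protocol's list. The practical effect depends on how many AEs are coded unknown, which the documents do not show and which may be zero. The mismatch touches one descriptive table in a 24-subject trial, and no efficacy result depends on it.

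**What to change.** 1. **Relatedness.** In Shell Table 6, replace the unlikely row with an unknown row. Alternatively, add unlikely to Protocol 10.1.2 and the CRF and still keep an unknown row. Either way the rows should sum to all AEs in each group. Replacement is simpler because it changes nothing that is collected.
2. **Severity.** Choose one of two forms and state it. Either use the four protocol grades and report deaths separately, or keep the fatal row, fill it from AE outcome or from the serious AE death criterion, and exclude those events from the life-threatening row so that no death is counted twice.
3. **Severity source.** Reconcile the CTCAE versions named in Protocol 10.1 and 10.1.1, and state how they relate to Table 5.

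The first two items cost a few edits to one shell and one sentence of derivation, and can be made before the final SAP is released for analysis. The third needs a small protocol correction, as does the first if unlikely is added to the protocol and CRF. No new data are needed if the unlikely row is simply replaced.
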